7.4 Detection of Bias

A factor that may bias the results of the study is major protocol deviations likely to impact the analysis and interpretation of the endpoints. Important protocol deviations likely to impact the analysis and interpretation of the endpoints will be tabulated in the Clinical Study Report (CSR).

If any sensitivity analyses are required to evaluate potential biases in the study's conclusions, the sources of the potential biases and results of the sensitivity analyses will be documented in the CSR.

7.5 Outliers

Various methods, including univariate summaries, histograms, scatter plots, box plots, and line graphs, will be used to identify outliers in key variables. Extreme data points will be identified during the review of the data prior to database snapshot. Such data points will be reviewed with clinical data management to ensure accuracy. Unless specified otherwise, all analyses will include outliers in the data. Sensitivity analyses may be undertaken if extreme outliers for a variable are observed.

7.6 Distributional Characteristics

There are no distributional requirements for the planned analyses. Therefore no assessment will be made.

7.7 Validation of Statistical Analyses

Programs will be developed and maintained, and output will be verified in accordance with current risk-based quality control procedures.

Tables, figures and listings will be produced with validated standard macro programs where standard macros can produce the specified outputs.

The production environment for statistical analyses consists of Amgen-supported versions of statistical analysis software, for example the SAS System.

8. Statistical Methods of Analysis

8.1 General Principles

Statistical analyses in this open-label extension study will be descriptive. Subject disposition, demographics and baseline characteristics will be summarized.

Summary statistics for continuous variables will include the number of subjects, mean, median, standard deviation or standard error, first and third quartiles, minimum, and maximum. For categorical variables, the frequency and percentage will be given.

All analyses will be carried out separately for the ICOAS and the IAAS analysis sets unless specified otherwise. There will be no imputation for missing data. Deaths and major cardiovascular events from this and other phase 3 studies will be adjudicated by an independent Clinical Events Committee (CEC) to facilitate aggregated analyses across the program. These events adjudicated by the CEC include:

- death by any cause
- cardiovascular death
- myocardial infarction
- hospitalization for unstable angina
- coronary revascularization
- stroke
- hospitalization for heart failure
- transient ischemic attack (TIA)

In addition, non-coronary revascularizations will be collected.

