10.4 Planned Methods of Analysis

10.4.1 General Approach/Considerations

Statistical analyses in this open-label extension study will be descriptive. Subject disposition, demographics and baseline characteristics will be summarized.

Summary statistics for continuous variables will include the number of subjects, mean, median, standard deviation or standard error, first and third quartiles, minimum, and maximum. For categorical variables, the frequency and percentage will be given. 95% confidence intervals will be calculated for select continuous and categorical endpoints.

Unless specified otherwise, the baseline value is defined as the subject's baseline value from the parent study. There will be no imputation for missing data.

Deaths and major cardiovascular events from this and other phase 3 studies will be adjudicated by an independent Clinical Events Committee (CEC) to facilitate aggregated analyses across the program. These events adjudicated by the CEC include:

- death by any cause
- cardiovascular death
- myocardial infarction
- hospitalization for unstable angina
- coronary revascularization
- stroke
- hospitalization for heart failure
- transient ischemic attack (TIA)

The CEC will adhere to a charter which details the adjudication process.

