Open Label Study of Long Term Evaluation Against LDL-C Trial

Amendment 1 Date : 12 February 2013

Amendment 2 Date: 30 April 2013

Superseding Amendment 2 Date: 23 May 2013

Amendment 3 Date: 15 November 2013

Superseding Amendment 3 Date: 15 February 2014

Superseding Amendment 3 Date: 24 February 2014

Amendment 4 Date: 15 April 2014

Amendment 5 Date: 19 December 2014

Amendment 6 Date: 03 April 2015

Rationale:

This document provides the rationale and detailed list of changes for Amendment 6, dated 03 April 2015, from Amendment 5 of the study protocol, dated 19 December 2014.

The purpose of the amendment is to:

- Update [exclusion criteria](#) to include methods of effective birth control in the protocol language

Description of Changes:

[Section: Header](#)

Replace:

19 December 2014

With:

03 April 2015

[Section: Coverage](#)

Add:

Amendment 6 Date: 03 April 2015

[Section: 4.2 Exclusion Criteria](#)

Second Criterion, Bullet point 2

Replace:

- Acceptable methods of effective contraception are defined in the ICF. Where required by local laws, regulations and/or guidelines, additional country-specific requirements are outlined in a country-specific protocol supplement.

With:

- **Acceptable methods of effective birth control include: sexual abstinence (when this is in line with the preferred and usual lifestyle of the subject [periodic abstinence (eg, calendar, ovulation, symptothermal, post-ovulation methods), declaration of abstinence for the duration of a trial, and withdrawal are not acceptable methods of contraception]), surgical contraceptive methods (vasectomy or bilateral tubal ligation), use of hormonal birth control methods (pills, shots, implants or patches), intrauterine devices (IUDs), or two (2) barrier methods (each partner must use one barrier method) with spermicide – males must use a condom with spermicide; females must choose either a diaphragm with spermicide, OR cervical cap with spermicide, OR contraceptive sponge with spermicide. Note: Additional medications given during treatment with evolocumab may alter the contraceptive requirements. These additional medications may require an increase in the number of contraceptive methods and/or length of time that contraception is to be utilized after the last dose of protocol-required therapies. The investigator is to discuss these contraceptive changes with the study subject.**

Amendment 5

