Title: A Multicenter, Controlled, Open-label Extension (OLE) Study to Assess the Long-term Safety and Efficacy of AMG 145

Amgen Protocol Number:20120138

EudraCT Number: **2012-004357-83**

OSLER 2

Open Label Study of Long Term Evaluation Against LDL-C Trial

Amendment 4 Date: 15 April 2014

Rationale:

This document provides the rationale and detailed list of changes for Amendment 4, dated 15 April 2014, from superseding amendment 3 of the study protocol, dated 24 February 2014.

The purpose of the amendment is to:

- Update the schedule of assessments schema for clarification and ease of use
- Add a patient questionnaire for patients experiencing a change in the device used to deliver AMG 145
- Minor other updates, clarifications and corrections

Amendment 3

Title: A Multicenter, Controlled, Open-label Extension (OLE) Study to Assess the Long-term Safety and Efficacy of AMG 145

Amgen Protocol Number: 20120138
EudraCT Number: 2012-004357-83

OSLER 2

Open Label Study of Long Term Evaluation Against LDL-C Trial

Goal Achievement after Utilizing an anti-PCSK9 antibody in Statin Intolerant Subjects

Amendment Date: 15 November 2013

Superseding Amendment Date: 15 February 2014

Superseding Amendment Date: 24 February 2014

Rationale:

This document provides the rationale and detailed list of changes for Amendment 3, dated 24 February 2014, from superseding amendment 2 of the study protocol, dated 23 May 2013.

The purpose of the amendment is to:

- Add Vitamin E reflex testing to the protocol in cases where LDL-C is < 25 mg/dL.
- Add language for the use of the 3.5 mL personal injector. The 3.5 mL Personal Injector will only be made available for use in this study once it has been determined that the intended user population for AMG 145 can safely and effectively use the device in clinical trials under guidance of study investigators.
- The schedule of assessments and schema were clarified and changed in format to be easier to use
- The body of the protocol and schedule of assessments were updated and made consistent
- The visit schedule was clarified to list the exact timing of the visit, replacing reference to quarterly visits
- The protocol now references the latest IB (2013)
- The protocol now includes "Investigator Responsibilities for Data Collection"
- Non-coronary revascularizations will no longer be collected (update to be consistent with DMC charter)
- Minor other updates, clarifications and corrections

Amendment 2 - Superseding Amendment

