IVRS	Interactive voice response system
LDL-C	Low density lipoprotein cholesterol
LFT	Liver Function Test
Lp(a)	Lipoprotein(a)
MedDRA	Medical dictionary for regulatory activities
OLE	Open label extension
QM	Every month
Q2W	Every 2 weeks
SOC	Standard of care
SAP	Statistical analysis plan
TIA	Transient ischemic attack
ULN	Upper limit of normal
VLDL-C	Very low density lipoprotein cholesterol

1. Introduction

The purpose of this interim SAP is to pre-specify interim analyses to support regulatory filings. The analysis strategy is consistent with the protocol specified analysis. Analyses will be performed based on datasets of an ongoing study 20120138, entitled A Multicenter, Controlled, Open-label (OLE) Study to Assess the Long-term Safety and Efficacy of AMG 145 (latest amendment 2 is 30 APR 2013).

2. Objectives

The objective for this analysis is to summarize the safety and lipid data collected up to a cutoff date reported in the table outputs for subjects rolled over from parent studies into the extension study 20120138. All data prior to the data cut date will be collected, checked and queried in the similar fashion as the final database lock.

3. Endpoints

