3.3 Exploratory Endpoints

- Subject incidence of adjudicated events and non-coronary revascularization
 - Death (all cause, cardiovascular)
 - Cardiac ischemic events (myocardial infarction, hospitalization for unstable angina, coronary revascularization)
 - Hospitalization for heart failure
 - Cerebrovascular events (transient ischemic attack, stroke)
 - Non-coronary revascularization
- Change and percent change from baseline and from parent study EOS at each scheduled visit in each of the following lipid and other lab parameters
 - Non-HDL-C
 - ApoB
 - Total cholesterol/HDL-C ratio
 - Total cholesterol

- ApoB/ApoA1 ratio
- Lp(a)
- Triglycerides
- HDL-C
- VLDL-C
- ApoA1
- High sensitivity C-reactive protein (hsCRP)

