8.4.3 Analyses of Exploratory Endpoints

All analyses will be performed separately by SOC-controlled period and All-IP period.

Subject incidence of adjudicated CV endpoints and non-coronary revascularization will be summarized.

The percent change and change from baseline in laboratory based exploratory endpoints at each scheduled visit will be summarized. For continuous exploratory endpoints, treatment group summary statistics (number of subjects, mean, median, standard deviation or standard error, first and third quartiles, minimum, and maximum) at all scheduled visits will be calculated.

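### The interim SAP still reports incidence of non-coronary revascularization after protocol Amendment 3 stopped collecting it, with no rule for follow-up in which it was not collected

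*SAP*

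**What the plan says.** SAP 3.3 lists among the exploratory endpoints "Subject incidence of adjudicated events and non-coronary revascularization". SAP 8.1 gives the eight event types adjudicated by the Clinical Events Committee (CEC) and adds: "In addition, non-coronary revascularizations will be collected". SAP 8.4.3 states "Subject incidence of adjudicated CV endpoints and non-coronary revascularization will be summarized", under the general instruction "All analyses will be performed separately by SOC-controlled period and All-IP period".

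Current protocol 10.4.1 introduces its list with "These events adjudicated by the CEC include" and names the same eight event types. It has no counterpart to the SAP's added collection sentence. The summary of changes for Amendment 3 gives the reason: "Non-coronary revascularizations will no longer be collected (update to be consistent with DMC charter". The amendment history dates the final version: "Superseding Amendment 3 Date: 24 February 2014".

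SAP Section 1 cites the protocol as "latest amendment 2 is 30 APR 2013", which is before that change. However, the laboratory windows in SAP Appendix A include Vitamin E, and the protocol's amendment history attributes Vitamin E testing to Amendment 3.

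**The concern.** The SAP promises a result on data that the protocol no longer gathers. All-IP data run to the earlier of end of study and data cutoff (SAP 5.1 and Section 6), and nothing in the SAP treats this event differently. A subject followed after collection ended therefore stays in the denominator, and an event that nobody recorded counts as no event.

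SAP Section 1 says these analyses support regulatory filings. A low count in this row could be taken as evidence that such events are rare, when it may only show that no one was asked to record them. All-IP follow-up is the later part of each subject's time, so it is the more exposed of the two.

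**Working it through.** The documents give no figure for this event, so there is none to reproduce. The check is date arithmetic.

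**Inputs**
- Earliest randomization: 12 February 2013. This is an assumption. It is the date of Amendment 1, which introduced the SOC group; the first-subject date is not given.
- Collection stop: 24 February 2014, the final date of Amendment 3. Its first version is dated 15 November 2013.
- All-IP start: the Week 48 dose, because the SOC-Controlled period ends the day before it (SAP 5.1). Week 48 is 336 days after Day 1, with a window of ±7 days (protocol 7.1.1.14).
- Site lag: unknown. Protocol 12.1 requires IEC/IRB approval of amendments. Assumed range: 0 to 180 days.
- Data cutoff: not given. SAP Section 2 leaves it to the table outputs.

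**Step 1: most All-IP collection any subject can have, zero lag**
- 12 February 2013 + 336 days = 14 January 2014, which is 41 days before 24 February 2014.
- With the visit 7 days early: 7 January 2014, which is 48 days before.
- At nominal visit timing, 24 February 2014 − 336 days = 25 March 2013. Subjects randomized on or after that date have none.
- With a stop on 15 November 2013, no subject has any.

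**Step 2: average coverage if every subject is followed to Week 104**

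Assume uniform enrolment from 12 February 2013 over L days, ending on 24 February 2014 (L = 377) or 19 December 2014 (L = 675). The All-IP period then lasts (104 − 48) × 7 = 392 days. With k = 41 + lag, covered share of All-IP time = (k²/2) / (392 × L).
- Zero lag: 840.5 / (392 × 377) = 0.57%; 840.5 / (392 × 675) = 0.32%.
- 90 days: k = 131, giving 5.8% and 3.2%.
- 180 days: k = 221, giving 16.5% and 9.2%.

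For the SOC-Controlled period, average min(336, days from randomization to stop), with a floor of zero, and divide by 336. At zero lag and L = 377 this is (41 × 336 + 336²/2) / (336 × 377) = 55.4%.

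| Site lag | All-IP time covered | SOC-Controlled time covered |
|---|---|---|
| 0 days | 0.3% to 0.6% | 31% to 55% |
| 90 days | 3% to 6% | 44% to 76% |
| 180 days | 9% to 17% | 58% to 90% |

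**Step 3: sensitivity to the cutoff**

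An early cutoff keeps only the earliest All-IP time, which is the best covered. With the same start and uniform enrolment, nominal Week 48 timing and a cutoff d days after 14 January 2014, the share is (k/d)², capped at 100%.
- Cutoff 1 April 2014 (d = 77): (41/77)² = 28% at zero lag. At 90 days' lag the stop is 25 May 2014, after the cutoff, so 100%.
- Cutoff 1 July 2014 (d = 168): (41/168)² = 6% at zero lag; (131/168)² = 61% at 90 days.

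**Step 4: ordering of the two periods**

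Within a subject, All-IP follow-up comes after SOC-Controlled follow-up. Any collection in the All-IP period therefore implies that the SOC-Controlled period was fully covered, and the reverse does not hold.

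**Step 5: later enrollees**

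Protocol 10.2 expects about 950 of 4428 subjects still to enrol (950/4428 = 21.5%). The sample size was updated at Amendment 5 (19 December 2014), 298 days after 24 February 2014. Within the assumed lag range these subjects have no collection in either period. Whether they enter this interim analysis depends on the cutoff.

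**The case against.** The strongest reply is that this is an interim SAP tied to Amendment 2, under which the row may have been correct. That explains how the text arose but does not remove the conflict, because the Vitamin E windows show that the SAP was revised with Amendment 3 content while this item stayed in. A partly updated SAP is the likeliest explanation.

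A second reply is that current protocol 10.4.1 is weak evidence. The SAP lists the same eight adjudicated events, the item was always additional to them, and the protocol body never says that collection stopped. This is fair. The explicit statement is in the amendment summary, which serves here to date the change. The mismatch itself is that the SAP asserts collection and the current protocol provides for none.

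A reader might go further and infer that the All-IP row is near zero by construction, or that 41 days is a hard maximum. The documents do not support either. The cutoff, first randomization date and site adoption dates are missing, the visit window alone moves 41 days to 48, and Step 3 spans 6% to 100%. With a very early cutoff every All-IP event row would be sparse, not only this one.

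A reader might also infer that the tables will favour AMG 145. No contrast between the periods is planned, the analyses are descriptive, and the loss within the SOC-Controlled period follows calendar date and not randomized arm. Worsening disease or hospitalization can still be reported as an adverse or serious adverse event (protocol 9.1.1 and 9.2.2), although the SAP does not route such reports into this row.

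**Conclusion.** The point holds as an inconsistency between the SAP and the protocol that leaves one exploratory row under-ascertained. Both periods are affected, the All-IP period probably more.

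On the assumed start of 12 February 2013 and zero site lag, the best-covered subject has about 41 to 48 All-IP days with collection. Average All-IP coverage to Week 104 is then below 1%, rising to 9% to 17% with a 180-day lag, and it could be much higher under an early cutoff. The size therefore cannot be fixed from the documents.

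No bias between arms is shown, and the primary and secondary endpoints are untouched. What remains is a risk of misreading: in tables meant for filings, a low count, above all in the All-IP period, could pass for a low event rate.

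**What to change.** Either of two changes to SAP 3.3, 8.1 and 8.4.3 would settle it.

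1. Remove non-coronary revascularization from all three sections.
2. Keep the row but restrict both numerator and denominator to follow-up before collection ended, state that end date in a footnote, and print 'not collected' for later follow-up. Because the measure is subject incidence, subjects whose period began after collection ended leave the denominator.

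A footnote alone would warn the reader but leave the denominator wrong. The second option needs a documented end date, by site if adoption differed; if the sponsor cannot supply one, the first is cleaner. The amendment cited in SAP Section 1 should be brought up to date at the same time.

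The cost is SAP wording and one exploratory row, either lost (with whatever valid early data it held) or restricted.

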8.2 Subject/Patient Accountability

The number and percent of subjects who were randomized, received IP, completed IP, discontinued investigational product and reasons for discontinuing, completed study, and discontinued study and reasons for discontinuing will be summarized by treatment group and for the SOC-controlled and All-IP periods separately as well as overall.

8.3 Demographic and Baseline Characteristics

All baseline tables will be summarized by randomized treatment and for all subjects in the ICOAS and IAAS. Baseline tables will summarize the following: baseline characteristics, demographics, cardiovascular medical history, and laboratory parameters.

8.4 Endpoint Analyses

8.4.1 Analyses of Primary Endpoint

The Medical Dictionary for Regulatory Activities (MedDRA) version 16.0 or later will be used to code all adverse events (AE) to a system organ class and a preferred term. All analyses will be performed separately for the ICOAS and IAAS analysis sets.

Subject incidence of adverse events, serious AEs, and AEs leading to withdrawal of investigational product, will be tabulated by system organ class and preferred term in descending order of frequency.

Summaries of adverse events and serious AEs occurring in at least 1% of the subjects by preferred term in any treatment arm will be provided in descending order of frequency.

Incidence of AEs related to a device will be tabulated by preferred term in descending order of frequency by treatment group.

Subject incidence of adverse events associated with lipid lowering therapies:

- **Diabetes-related**
- **Muscle-related**
- **Liver-related**

associated with injectable protein therapies:

- **Injection site reactions**
- **Hypersensitivity or allergic reactions**

and potential hepatitis C infections will be summarized by category and preferred term.

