9.1.2 Reporting Procedures for Adverse Events

The investigator is responsible for ensuring that all adverse events observed by the investigator or reported by the subject that occur after enrollment through the EOS are reported using the applicable eCRF (eg, Adverse Event Summary eCRF).

The investigator must assign the following adverse event attributes:

- Adverse event diagnosis or syndrome(s), if known (if not known, signs or symptoms)
- Dates of onset and resolution (if resolved),
- Severity
- Assessment of relatedness to IMP: AMG 145
- Assessment of relatedness to the device (prefilled Autoinjector/Pen (AI/Pen) or 3.5 mL Personal Injector), or other protocol-required therapies
- Action taken

The adverse event grading scale used will be the NCI Common Terminology Criteria for AEs (CTCAE) grading scale. The toxicity grading scale used in this study is described in [Appendix B](#).

The investigator must assess whether the adverse event is possibly related to AMG 145 and/or other protocol-required therapies. This relationship is indicated by a “yes” or “no” response to the question: Is there a reasonable possibility that the event may have been caused by AMG 145 and/or other protocol required therapies?

The investigator must assess whether the adverse event is possibly related to the prefilled AI/pen or 3.5 mL Personal Injector device used to administer IMP: AMG 145. The relationship is indicated by a “yes” or “no” response to the question: Is there a reasonable possibility that the event may have been caused by the device?

The investigator must assess whether the adverse event is possibly related to any other study-mandated activity or procedure. This relationship is indicated by a “yes” or “no” response to the question: “Is there a reasonable possibility that the event may have been caused by a study activity/procedure”?

The investigator is responsible for reviewing laboratory test results and determining whether an abnormal value in an individual study subject represents a clinically significant change from the subject's baseline values. In general, abnormal laboratory findings without clinical significance (based on the investigator's judgment) should not be recorded as adverse events. However, laboratory value changes that require treatment or adjustment in current therapy are considered adverse events. Where applicable, clinical sequelae (not the laboratory abnormality) should be recorded as the adverse event.

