9.2 Serious Adverse Events

9.2.1 Definition of Serious Adverse Events

A serious adverse event (SAE) is defined as an adverse event that meets at least 1 of the following serious criteria:

- fatal
- life threatening (places the subject at immediate risk of death)
- requires in-patient hospitalization or prolongation of existing hospitalization
- results in persistent or significant disability/incapacity
- congenital anomaly/birth defect
- other medically important serious event

An adverse event would meet the criterion of "requires hospitalization", if the event necessitated an admission to a health care facility (eg, overnight stay).

If an investigator considers an event to be clinically important, but it does not meet any of the serious criteria, the event could be classified as a serious adverse event under the criterion of "other medically important serious event". Examples of such events could include allergic bronchospasm, convulsions, blood dyscrasias, drug-induced liver injury (see [Appendix B](#)) for drug-induced liver injury reporting criteria, or events that necessitate an emergency room visit, outpatient surgery, or urgent intervention.

If adverse events correspond to grade 4 “life threatening” CTCAE (eg, laboratory abnormality reported as grade 4 without manifestation of life threatening status), it will be left to the investigator’s judgment to also report these abnormalities as serious adverse events. For any adverse event that applies to this situation, comprehensive documentation of the event’s severity status must be recorded in the subject’s medical record.

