Appendix B. Additional Safety Assessment Information

Adverse Event Toxicity Grading Scale

Refer to the NCI Common Terminology Criteria for AEs (CTCAE) Version 4.0 for AE grading and information. The CTCAE is available at the following link:

http://ctep.cancer.gov/protocolDevelopment/electronic_applications/ctc.htm.

Drug-induced Liver Injury Reporting & Additional Assessments

Reporting

To facilitate appropriate monitoring for signals of DILI, cases of concurrent AST/ALT and TBL elevation according to the criteria specified in [Section 6.1.3.2](#) (3x ULN for AST/ALT and 2x ULN for TBL or INR>1.5 ULN) require the following:

- The event should be reported to Amgen as a serious adverse event within 24 hours of discovery or notification of the event (ie, before additional etiologic investigations have been concluded)
- The appropriate eCRF (eg, adverse event eCRF) that captures information necessary to facilitate the evaluation of treatment-emergent liver abnormalities should be completed.

Other events of hepatotoxicity and potential DILI should be reported as serious adverse events if they meet the criteria for a serious adverse event defined in [Section 9.2.1](#).

Additional Clinical Assessments and Observation

All subjects in whom IP is withheld due to potential DILI or who experience AST/ALT elevations >3x ULN should undergo a period of “close observation” until abnormalities return to normal or to the subject’s baseline levels. Assessments that should be performed during this period include:

- Repeat liver chemistries within 24-48 hours (ALT, AST, ALP, TBL); in cases of TBL >2x ULN or AST/ALT much greater than 3x ULN, retesting should be performed within 24 hours
 - Subjects should be monitored at least twice weekly; testing frequency may decrease to once per week or less if laboratory abnormalities stabilize or the IP has been discontinued AND the subject is asymptomatic
- Obtain PT/INR, fractionated bilirubin and any other potentially relevant laboratory evaluations of liver function or disease
- Obtain complete blood count (CBC) with differential to assess for eosinophilia
- Obtain appropriate blood sampling for pharmacokinetic analysis if this has not already been collected

- Obtain a more detailed history of:
 - Prior and/or concurrent diseases or illness
 - Exposure to environmental and/or industrial chemical agents

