3.1 Primary Endpoint

Subject incidence of Adverse Events (AEs).

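### Every adverse event is graded by CTCAE, but no planned adverse event table uses the grade, so severe events that are non-serious and do not stop investigational product count the same as mild ones

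*SAP*

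**What the plan says.** Severity is one of the attributes that Protocol 9.1.2 obliges the investigator to assign to each adverse event, and the scale is fixed: "The adverse event grading scale used will be the NCI Common Terminology Criteria for AEs (CTCAE) grading scale". Appendix B gives the version: "Refer to the NCI Common Terminology Criteria for AEs (CTCAE) Version 4.0 for AE grading and information".

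The primary endpoint has no severity threshold. SAP 3.1 gives it as "Subject incidence of Adverse Events (AEs"), and Protocol 10.1.1 agrees.

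The planned adverse event tables in SAP 8.4.1 are:

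- "Subject incidence of adverse events, serious AEs, and AEs leading to withdrawal of investigational product, will be tabulated by system organ class" and preferred term;
- "Summaries of adverse events and serious AEs occurring in at least 1% of the subjects by preferred term in any treatment arm will be provided";
- "Incidence of AEs related to a device will be tabulated by preferred term in descending order of frequency by treatment group";
- diabetes-, muscle- and liver-related events, injection site reactions, hypersensitivity, "and potential hepatitis C infections will be summarized by category and preferred term".

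Protocol 10.4.2.1 plans all events, serious events and events leading to withdrawal, by system organ class and preferred term, with subgroups by parent study. Neither section mentions grade. CTCAE enters the analysis only through the laboratory shift tables (Protocol 10.4.2.4, SAP 8.4.4). SAP 8.4.4 also counts subjects above fixed CK, ALT/AST and bilirubin thresholds.

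**The concern.** The primary objective is safety and tolerability, and tolerability depends on how bad events are as well as on how many subjects have one. A subject with a mild and a subject with a severe episode of the same preferred term each add one to the same row.

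Suppose AMG 145 made some events worse without making more subjects have them: muscle pain of grade 3 where it would otherwise have been grade 1, non-serious and not stopping treatment. Every planned adverse event table would look the same in the two arms. The data to show the difference would be in the database, but no specified output would use them.

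**Working it through.** **1. Is grade used in any adverse event table?** Going through Protocol 10.4.2.1 and SAP 5.3, 7.3.3 and 8.4.1 gives 0 adverse event analyses by grade in the protocol and 0 in the SAP.

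**2. Does another planned table stand in for grade?**

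- *Serious events.* Seriousness and severity are separate. For a grade 4 event without manifest threat to life, Protocol 9.2.1 says "it will be left to the investigator" to judge whether to report it as serious as well. A grade 3 event that meets no serious criterion has no route into that table.
- *Withdrawal.* The SAP counts withdrawal of investigational product. SOC-alone subjects receive none before Week 48, so in the SOC-Controlled period their count is zero by construction. The row cannot compare severity between arms in the only randomized period.
- *Laboratory analyses.* Shift tables and threshold counts show severe laboratory abnormalities for the chosen analytes. They say nothing about the severity of symptoms such as muscle pain, injection site reactions or hypersensitivity.

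**3. The plan's own precision figure.** Inputs from Protocol 10.2 and the synopsis: 3478 + 950 = 4428 subjects, randomized 2:1, so 2952 and 1476. Exact (Clopper-Pearson) 95% intervals at a 5% incidence:

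- SOC-alone, 74/1476: 3.96% to 6.25%; stated (4.0%, 6.3%).
- AMG 145 + SOC, 148/2952: 4.25% to 5.86%; stated (4.3%, 5.9%).

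Both reproduce. The point does not depend on them, but they fix the arm sizes.

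**4. What a grade 3 or higher row could show (illustration).** The documents give no such rate, so all rates here are assumed. With d = p1 − p0 and SE = √[p1(1−p1)/n1 + p0(1−p0)/n0], the probability that the 95% interval for the difference lies above 0 is about Φ(d/SE − 1.96).

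For 4.5% versus 3%:

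- Full size, 2952 versus 1476: SE = √(0.042975/2952 + 0.0291/1476) = 0.00585; d/SE = 2.56; Φ(0.60) = 0.73. Simulating the interval gives 0.72. Extra subjects: 2952 × 0.015 = 44.
- The 3478 already enrolled, taken as 2:1 (2319 versus 1159): SE = √(0.042975/2319 + 0.0291/1159) = 0.00661; d/SE = 2.27; Φ(0.31) = 0.62.

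The same formula for a 1.5-fold rate over a range of base rates:

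| SOC-alone | AMG 145 + SOC | 2952 vs 1476 | 2319 vs 1159 |
|---|---|---|---|
| 2% | 3% | 0.55 | 0.45 |
| 3% | 4.5% | 0.73 | 0.62 |
| 4% | 6% | 0.85 | 0.75 |
| 5% | 7.5% | 0.92 | 0.84 |

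A pooled-variance test gives slightly lower values at full size (0.68 at the 3% base rate). That is a difference of method.

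**5. What the planned rows show for the same events.** If the 44 subjects would have had the same preferred term at a lower grade, and the events are non-serious and do not stop treatment, every planned adverse event row is unchanged.

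**The case against.** The strongest reply is that the gap is narrow, and much of this stands.

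- A reader might infer that any excess of severe adverse events would be missed. The documents do not support that. Serious events and events stopping investigational product have their own tables, and Protocol 9.2.1 lets investigators class as serious an event needing an emergency room visit, outpatient surgery or urgent intervention.
- A reader might also infer that equal overall incidence makes every row equal. It does not. Extra severe events in subjects who would not otherwise have had that preferred term raise its row, and perhaps its category. A zero difference throughout requires a pure change of grade within the same preferred terms.
- Nor is a grade 4 laboratory event confined to the overall row. If recorded as an adverse event, it also appears under its system organ class and preferred term and, where it applies, in the muscle or liver category. The value itself can reach the shift tables and threshold counts.
- The rates are assumed, and the arm sizes are not those of the SAP's analysis. That SAP is interim, written against Amendment 2, and limits the SOC-Controlled set to subjects with more than 91 days of potential follow-up at the cutoff. The 4428 comes from a later amendment and includes about 950 subjects not yet enrolled.
- No final SAP is among the documents, so final reporting might include grade. Protocol 10.4.2.1, which governs both, has the same omission.
- Severity is judged by investigators who know the arm, so a graded contrast carries open-label reporting bias too.

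These points limit the consequence. None supplies a planned table in which a severe, non-serious symptomatic event is told apart from a mild one.

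**Conclusion.** The point holds in a limited form. Grade is collected for every adverse event and used in no planned adverse event table. The group lost from view is severe events that are non-serious and do not lead to withdrawal of investigational product. A shift towards greater severity within the same preferred terms would not show in the adverse event tables. Severe laboratory abnormalities are partly covered elsewhere.

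The size can only be illustrated. Under the assumed 3% versus 4.5%, a grade 3 or higher row would give an interval excluding 0 with probability about 0.72 at full size and 0.62 with those already enrolled. The interim set's size is not stated. The analyses are descriptive, so no planned estimate is wrong and no test, error rate or sample size is affected. The change is still worth making, because it bears directly on the tolerability part of the primary objective.

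**What to change.** Add to SAP 8.4.1 and Protocol 10.4.2.1:

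- subject incidence of adverse events by worst CTCAE grade, each subject counted once at the highest grade;
- subject incidence of adverse events of grade 3 or higher;
- both overall, by system organ class and preferred term, and within the named categories (diabetes-, muscle- and liver-related events, injection site reactions, hypersensitivity, potential hepatitis C infection).

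Show these by arm for the SOC-Controlled period and separately for the All-IP period. Add a note that investigators graded severity knowing the arm, and that the SOC-alone count for withdrawal of investigational product is zero by construction in the SOC-Controlled period.

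The cost is a few standard tables from a field already on the form, and longer output. No new data, visits or subjects are needed, and no rule for treating subjects changes.
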